- When to return for the day 49 (42 days post-removal) visit to assess healing. And the importance of returning for that assessment.
- The importance of good hygienic practices while the wound heals, and how to keep the penis and wound clean and free of potential infection, including the importance of tetanus mitigation strategies.
- The client will be instructed to return to the evaluation site in case of any unexpected event, for example if there is severe discoloration of the penis, signs of infection (purulence), severe or increasing pain, or any other significant concern they may have.
- The client will be advised that painful erections may occur during the night.
- All clients will be provided with a phone number for the facility, and encouraged to call any time with any questions or concerns.
- All sexually active clients will be offered a package of condoms to take home.
- The importance of continued abstention from sex or masturbation for 6 weeks (42 days), following the removal of the ShangRing device, or until the penis is fully healed (whichever comes last).

Key Post-Device Removal Counseling during AE Assessment Call

Three days following the removal of the ShangRing, all clients will receive a phone call to assess for symptoms of AEs. If the client is determined to be exhibiting signs of an AE, they will be advised to immediately return to the site that performed the circumcision for treatment. During this call, implementation pilot staff will also remind clients of the following:

- The importance of good hygienic practices while the wound heals, and how to keep the penis and wound clean and free of potential infection, including the importance of tetanus mitigation strategies.
- The client will be reminded to return to the evaluation site in case of any unexpected event, for example if there is severe discoloration of the penis, signs of infection (purulence), severe or increasing pain, or any other significant concern they may have.
- The client will be reminded that painful erections may occur during the night.
- All clients will be reminded that they are encouraged to call any time with any questions or concerns.
- The importance of continued abstention from sex or masturbation for 6 weeks (42 days), following the removal of the ShangRing device, or until the penis is fully healed (whichever comes last).
- When to return for the day 49 (42 days post-removal) visit to assess healing. And the importance of returning for that assessment.

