Follow-Up Visits

Active follow-up will be initiated for clients who fail to return on day 7 post-placement to have the device removed, or for other visits (e.g. AE follow-up) recommended by the ShangRing clinician. Each implementing site will assign staff to conduct follow-up telephone calls and home visits as needed. All active follow-up efforts will be documented on the appropriate forms designed for this purpose (Appendix XI). For clients who fail to return for device removal on day 7, active follow-up will start on day 8. Active follow-up will start with telephone calls to the contact number(s) provided by client and recorded on the locator information sheet at enrolment. An

introductory script for contacting clients by phone is attached as Appendix X. If a client is not reachable through direct voice calls, short text message reminders will be sent to his contact phone number. The reminder text message will include client name and specify the name and phone number of the clinic reaching out to him. The text message will not include the purpose of appointment visit for which the reminder is sent. Up to five calls will be made to reach the client; one per day starting on day 8, and continuing over the next 4 days through Day 12 (5 days post-procedure).

Once contact is made, the staff member will reinforce the importance of device removal and encourage the client to return to the circumcision site. If the client states that he is not able to return by day 9 post-placement, or the schedule day, or does not in fact return by day 9 or the schedule day, the staff member will attempt to verify the addresses provided to schedule an appointment at one of the address locations provided for device removal on day 9, or as soon as possible. If the client has not been successfully contacted by day 9 or the scheduled day, home tracing visits to the address he provided will begin. These will total up to 4 visit attempts on different days if necessary to reach the client.

For clients not under follow-up for AEs who miss scheduled visits other than the day 7 visit, follow-up will be done through phone by text messages or voice calls only, except in exceptional circumstances where a clinician deems physical follow-up necessary.

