The staff member will discuss the clinical course and AE with the client and encourage the client to return for review to the health facility where the circumcision procedure was performed, if deemed medically necessary. If the client does not return for follow-up visits deemed medically indicated, active tracing will be initiated. In situations where clients cannot be reached by telephone or located through physical tracing, after a total of 8 calls and 4 visits on different days, the case will be directed to the attention of the site manager for disposition. In this case, these clients will be considered to have experienced a moderate AE by default, unless follow-up indicating otherwise is able to be completed.

In-Person Qualitative Interviews

The evaluation staff will select 50 individuals to participate in a more in-depth in-person qualitative interview to be held 28 days post-circumcision. Fifty clients were chosen as the sample size, based on prior experience with evaluating acceptability of circumcision devices, which suggests that 50 is sufficient to obtain the necessary range of views and opinions. Only males aged 18 years or older will be eligible to be selected to participate in the qualitative interviews. All clients will be asked when they are enrolled if they are willing to participate in an interview. The first 50 clients, aged 18 years or older, to indicate willingness at enrollment to participate will be asked to interview. If after contacting these men for an interview, not all are able to participate, clinic staff will

continue to proceed down the list of clients in the order in which they enrolled and agreed to an interview, until 50 clients are selected. These interviews will be used to assess client pain, discomfort, and satisfaction with the procedure. Males selected for the qualitative interviews may refuse to participate or withdraw at any time, the reason for their refusal/withdrawal will be recorded and reported. Clients will be offered a small amount to reimburse their travel and time spent for the interview (estimated to be between 20-25 USD/45,000-56,500 Tanzanian Shillings but not to exceed 30 USD/67,900 Tanzanian Shillings).

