Baseline demographics and client characteristics will be presented in tabular format using descriptive statistics. Binary data such as adverse events will be presented as counts and percentages and the upper limit of the estimate of the AE rate (percent of clients with one or more AE) will be based on a two-sided 95% confidence interval. Adverse event rates will be compared descriptively with the reported rates of similar treatments reported in Tanzania and elsewhere, including: comparison against AE rates found in other studies of ShangRing, comparison against AE rates found in studies of other circumcision devices, and comparison against reported rates of AEs in studies of surgical circumcision. No formal hypothesis tests will be done comparing AE rates in this evaluation to other AE rates.

Adverse event rates will be presented by seriousness, severity, relation to device and outcome by site and by cadre. Continuous data will be represented by a mean, standard deviation, median, minimum and maximum together with 95% confidence intervals for the means. The number and percent of subjects who fail to complete the evaluation will be assessed. Time to withdrawal may also be assessed. The procedure time will be calculated. The first 15 procedures performed by each provider will be compared to the last 15 procedures by that provider with respect to procedure time, to evaluate whether procedure time is shortened with experience. All of the first and last 15 procedures evaluated will take place during the main implementation pilot phase. If a provider does not perform 30 total procedures following the training phase, then the first half of the total number of procedures performed will be compared against the last half. Adverse event rates from the training and post-training phases will also be reported, as well as an overall AE rate. Procedure times during the provider training phase will be tracked, but not used for comparisons. The differences in mean procedure times will be compared with a t-test or a non-parametric equivalent.

Standard statistical software packages R, Stata or SAS will be used for the analysis. No corrections for missing values will be imputed. The data will be analyzed and presented “as-is”.

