Appendix XIV – ShangRing Adverse Event Day 3 Post-Removal AE Check-in Call Form

ShangRing Adverse Event Check-in Call Form

Client ID:

Instructions

This form is to be used during the call with clients to check for signs of adverse events three days following the removal of the ShangRing device. The questions below are meant to evaluate whether the client is potentially experiencing an adverse event in the aftermath of their circumcision. After introducing yourself, and informing the client of the purpose of the call, ask the client each question on the list. For any 'yes' answers, probe for more information. If any of the information the client offers suggests an adverse event, advise that the client come to the clinic immediately for further evaluation.

Questions

1. Are you experiencing pain that keeps you from doing anything you normally do? **Y** **N**

a. **If yes:** Advise the client to visit the clinic to be evaluated

Note any comments: _____

2. Has swelling, tenderness or pain around the wound gotten worse since your circumcision? **Y** **N**

a. **If yes:** Advise the client to visit the clinic to be evaluated

Note any comments: _____

3. Have you noticed any expanding redness around the wound area, or red streaking spreading from the wound? **Y** **N**

a. **If yes:** Advise the client to visit the clinic to be evaluated

Note any comments: _____

4. Have you noticed any pus or fluid coming from the wound area? **Y** **N**

a. **If yes:** Advise the client to visit the clinic to be evaluated

Note any comments: _____

5. Have you felt like you have had a fever in the past few days, or experienced chills, shaking, breaking into sweats more than usual? **Y** **N**

a. **If yes:** Advise the client to visit the clinic to be evaluated

Note any comments: _____

6. Are you still bleeding from the wound area? **Y N**

a. **If yes:** Advise the client to visit the clinic to be evaluated

Note any comments: _____

7. Are you experiencing any difficulty urinating? **Y N**

a. **If yes:** Advise the client to visit the clinic to be evaluated

Note any comments: _____

8. Are you experiencing any other new problems since the surgery? **Y N**

a. **If yes:** Ask the client to describe the symptoms, and record below. If the symptoms are concerning advise the client to visit the clinic to be evaluated.

Note any comments: _____

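### A client who reports AE symptoms on the staff's day-10 call and is never examined has no counting rule, while an untraceable client who phoned in himself is scored as a moderate AE

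*Protocol*

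**What the plan says.** **Client-initiated calls** (Protocol, Telephone Calls Initiated By Clients due to AEs). Staff discuss the event and encourage a visit if it is medically necessary. "If the client does not return for follow-up visits deemed medically indicated, active tracing will be initiated". Once the stated calls and home visits have failed, the case goes to the site manager, and "these clients will be considered to have experienced a moderate AE by default"; later follow-up that shows otherwise can reverse this.

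**The staff's day-10 call** (Key Post-Device Removal Counseling during AE Assessment Call). "If the client is determined to be exhibiting signs of an AE, they will be advised to immediately return to the site". The call form in Appendix XIV says the same: "If any of the information the client offers suggests an adverse event, advise that the client come to the clinic immediately for further evaluation". It has yes/no symptom items and comment lines, but no field for an AE decision and none for whether the man came in.

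**Endpoint and documentation.** Primary Endpoint lists three days post-removal among the assessment times. Data Collection provides for AE forms at day 0, day 7, day 49 and unscheduled visits; for the day-10 call it lists only the interview.

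**Tracing** (Follow-Up Visits). Active follow-up starts for men who miss device removal "or for other visits (e.g. AE follow-up) recommended by the ShangRing clinician".

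**Analysis.** Procedure for Handling Clients Lost-to-Follow-Up takes out of the AE calculation only men who did not return for removal. Analysis Overview defines the AE rate as the percentage of clients with at least one AE, and adds: "No corrections for missing values will be imputed".

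**The concern.** The two calls can produce the same evidence: symptoms described by telephone and never seen by a clinician. In one case the protocol assigns a moderate AE; in the other it assigns nothing. Two analysts who both follow the protocol could report different primary rates from the same data.

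The default also supplies an outcome that nobody observed, and the analysis section rules out imputation without mentioning it. An analyst cannot tell which of the two statements governs.

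This matters because the primary endpoint is a proportion expected to be about 2%, so it rests on about a dozen clients. A few differently scored men would move it visibly. The call form also does not capture attendance, and that gap cannot be reliably repaired after data collection.

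**Working it through.** **1. Where the day-10 man ends up.** Take a man whose ring was removed on day 7, who answers yes to a symptom item on day 10, does not attend, cannot be traced and is not examined at day 49.

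- Exclusion: the lost-to-follow-up rule does not reach him, because he returned for removal. Follow-Up Visits labels a man who misses day 49 as lost, but attaches no counting rule to the label.
- Default moderate AE: its heading limits it to client-initiated calls.
- AE form: Data Collection lists none for the day-10 call, Appendix XIV has no AE field, and the visit types in Appendix XII do not include that call.
- Imputation: none, by Analysis Overview.

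The likely result is that he stays in the denominator and out of the numerator. This is an inference from four silences; no sentence says it.

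**2. The plan's own precision figure.** Inputs from Sample Size, Data Collection and Analysis Timeline: p = 0.02, half-width d = 0.015, 95% confidence.

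n = 1.96² × 0.02 × 0.98 / 0.015² = 334.6, rounded up to 335, which matches the protocol. At N = 575 the half-width is 1.96 × √(0.02 × 0.98 / 575) = 1.14 points.

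**3. Weight of one man.** 1/575 = 0.17 points. Seven men (7/575 = 1.22 points) would exceed that half-width.

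**4. Effect of the counting rule.** At a 2% rate, 0.02 × 575 = 11.5, taken as 12 recorded AE clients. The number k of unexamined day-10 reports is assumed. Intervals are exact (Clopper-Pearson) 95%.

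| k (assumed) | Scored without an AE | Scored as AE by the default |
|---|---|---|
| 1 | 12/575 = 2.09% (1.08 to 3.62) | 13/575 = 2.26% (1.21 to 3.84) |
| 3 | 2.09% | 15/575 = 2.61% (1.47 to 4.27) |
| 6 | 2.09% | 18/575 = 3.13% (1.87 to 4.90) |

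Excluding the men instead barely moves the rate: for k = 6, 12/569 = 2.11%.

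For scale, k = 575 × (share with symptoms at day 10) × (share of those never examined). Both shares are assumptions: 2% and 10% give 1.2 men, 5% and 10% give 2.9, and 2% and 50% give 5.8.

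**5. Direction.** Let a be the men with a true AE who are left without one after the day-10 call, and b the men without a true AE whom the default scores as moderate. The net error in the rate is (b − a)/575. The protocol gives neither a nor b, so the sign is open.

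**The case against.** A reader might infer that the protocol counts the day-10 man as AE-free and so biases the primary rate low. The documents do not support that:

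- No passage says it. The follow-up form in Appendix XII accepts a telephone contact and asks about an AE seen or reported, so staff could record one from the call alone.
- Active follow-up covers missed AE visits recommended by the clinician, whoever placed the call, so a positive day-10 call need not end with advice.
- All men are called back at day 49, when AEs are documented. Only a man who ignores the advice, escapes tracing and also misses day 49 is affected.
- The default adds AEs that nobody examined, so its own error can run upward.

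All of this stands. It reduces the number of men concerned and removes any claim about direction. It does not supply a counting rule, since tracing and a chance to record an event do not say how a man counts when both fail.

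It can also be argued that only a heading ties the default to client calls, so it may be meant generally, or that it classifies an endpoint rather than imputes a missing value. Either reading is reasonable, but the text does not state it, and the reader should not have to choose.

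A reader might also see a conflict in call limits, since Follow-Up Visits says "Up to five calls will be made to reach the client; one per day starting on day 8" while the default requires eight calls. The five calls are for missed device removal, so the two counts serve different situations. Nor does the protocol show that day-10 reporters outnumber client callers.

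Lastly, a second AE rate is something a statistical analysis plan could hold, and that document is not at hand. The scope of the default, its tension with the no-imputation rule and the missing field on the call form are nevertheless fixed in the protocol.

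**Conclusion.** The point holds as an unstated and uneven counting rule for the primary endpoint. The protocol assigns an outcome to one group of unexamined telephone reports and leaves the other without one, and it does not reconcile that assignment with its no-imputation statement. It should be corrected because the cost is small. It does not show that the reported rate will be too low.

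Each man scored one way rather than the other moves the rate by 0.17 points. Starting from 2.09%, an assumed 1 to 6 men would give 2.26% to 3.13%. These figures rest on a denominator of 575, 12 recorded AE clients, and a number of unexamined day-10 reporters that the protocol does not give. AE rates are compared with other studies only descriptively, so no formal test depends on the choice, but the headline safety figure and its upper confidence limit do.

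**What to change.** 1. In Analysis Overview, state one counting rule for every client who reports AE symptoms by telephone and is never examined afterwards, whoever placed the call. For the day-10 call, let the advice to attend be the trigger. Keep the existing provision that later follow-up can reverse the classification, and apply it to both groups.
2. Name this rule there as the exception to the no-imputation statement, and cross-refer to it from the sections on client-initiated calls, the day-10 call and lost clients.
3. Report the AE rate twice: confirmed AEs only, and confirmed AEs plus unexamined reports classed by the existing moderate-AE default. Say in advance which is the headline rate.
4. Add one line to Appendix XIV: advised to attend, with the outcomes attended, not attended and AE confirmed.

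The cost is protocol wording, one form line and one extra table row. The downside is that the second rate may count some men who had no AE, which is why both rates are shown.

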 - A description of each adverse event by type, severity, time of detection (days post-application and/or post-removal) captured as date AE is diagnosed, clinical management, and resolution. The likelihood of relatedness to having undergone VMMC and relatedness specifically to the ShangRing device will be determined. AEs will be defined using the definitions in the second edition of the VMMC Adverse Event Action Guide.²⁴ These are specific to each AE type, but in general:
 - Mild: classification indicates minimal or no intervention is required beyond reassurance and observation;
 - Moderate: classification relates to those AEs that are neither mild nor severe, require intervention, and are usually managed on-site;
 - Severe: classification requires extensive intervention with referral or specialist input.
 - Note: a Serious Adverse Event (SAE) is a standard definition used across many types of interventions. In the context of VMMC, all AEs that meet criteria for severe should also be classified as SAEs. In addition, SAEs also include any event that:
 - Results in death

- Is life threatening
- Requires intervention to prevent permanent disability or incapacitation (including deformity), or results in permanent disability or incapacitation (including deformity)
- Requires hospitalization or referral to a specialist for higher level care or intervention.
- (Note: device displacement is included as an AE both in the moderate and severe classifications – see Appendix XV).

Secondary Endpoints

- Determine the training needed for proficiency, including number of procedures required under supervision to become certified as fully proficient. This will involve analyzing AE rates stratified by during training and post-training in addition to overall.
 - Determining whether various cadres are trainable as safe providers. This would involve analyzing AE rates stratified by provider cadre.
- Document client acceptability and satisfaction, to be measured by the following:
 - Time for client to return to normal activity, including work and routine tasks.
 - Clients' opinions of convenience (having device applied, 'wearing' the device for a week, and returning for device removal), acceptability, cosmetic result, and whether they would recommend VMMC, and specifically the ShangRing VMMC option to others.

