AE and other incidents that occur as a result of the ShangRing device will be recorded as part of this evaluation. All events and incidents – including mild, moderate and severe AE, expected side effects such as common post-operative findings, occurrences resulting from clients' failure to follow instructions, and device malfunctions – will be documented on the appropriate visit section and device-related events form of the CRF. Events classified according to the definitions provided as mild, moderate and severe based on the PEPFAR AE definitions below should also be recorded on the adverse events form of the CRF. The adverse events form will include a description of the onset, duration, relationship to the procedure, severity, seriousness, and final outcome of the AE. For additional information on severity criteria by type of AE see Appendix XV.

For the purposes of this evaluation AEs that are related to the evaluation device will be graded using the following definitions as guides:

- Definitely related: direct association with the procedure, i.e., follows a reasonable temporal sequence and is a recognized AE of the procedure. Note that this does not imply any error on the part of the provider or client, only that the event would not have happened if the procedure had not been performed.
- Likely/possibly related: more likely explained by the procedure, i.e., follows a reasonable temporal sequence from the procedure and is a plausible AE of the procedure, but could have another cause.
- Likely unrelated: more likely explained by another cause.
- Definitely unrelated: clearly explained by another cause.

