A physician will evaluate each AE for severity, seriousness, and relationship to the MC procedure, per the categories and criteria delineated in the *AE Action Guide for Voluntary Medical Male Circumcision by Surgery or Device, 2nd Edition* (see Appendix XV for table of AEs and severity). To ensure objectivity, the evaluating physician will be brought in from a site other than where the circumcision was performed. Any evaluating physician should be trained in male circumcision, and have experience evaluating adverse events. Methods to assess the severity, seriousness and relatedness of the AE are detailed in the evaluation SOP manual. Evaluation physicians will be trained to make these assessments in a manner as standardized as possible. The site coordinator will verify that this information will be captured during every evaluation subject visit. AEs will be managed medically as appropriate, and will be followed until resolution or until a clinically stable endpoint is achieved.

The incidence and severity of all AEs related to the circumcision procedure will be documented and collected on the appropriate visit section and device-related events form of the CRF. This form will include a description of the onset, duration, relationship to the procedure, severity, seriousness, and final outcome of the AE. Severe and serious AEs, as well as AEs related to client self-removal of the ShangRing, will also be documented on the ShangRing Device Related Adverse Events form (see Appendix XIV), which must be completed for all AEs that result in hospitalization and all AEs classified as severe per the AE classification guidelines, as well as for those whose severity cannot be classified. The evaluation will compile and analyze mild, moderate and severe AE to determine the AE rate. All other device-related events, including expected side effects and occurrences resulting from clients' failure to follow instructions, will be compiled and summarized to inform program policy related to ShangRing use.

For the purposes of this evaluation, **all** severe AEs must be reported to the CDC **within 24 hours of notification**. Standard reporting procedures for all **notifiable** AEs must be followed per PEPFAR and national guidelines.

ShangRing and Tetanus

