Appendix XVIII – Adverse Event Reporting Form

Client ID:

Device Related Events Form

Has the participant experienced a device related event per protocol? This includes mild, moderate and severe AE, expected side effects such as common post-operative findings, occurrences resulting from participants' failure to follow instructions, and device malfunctions. Please consult the *Adverse Event Classifications and Definitions: During Device Placement or Wearing and During or After Device Removal* for clarification and definition of adverse events. If the client is determined to have experienced an adverse event, please complete below.

If this is an AE defined as moderate or severe, also fill in the corresponding AE form. Note, that notifiable adverse events must also be reported also per PEPFAR and national guidelines.

Client ID:

Device Events Form

Device Event (Indicate type)	Evaluation Phase	Start/Onset
 Anesthetic Related Problem	During placement  While in place  (before discharge)	Date:
 Bleeding	During removal  After removal 	Time:
 Pain		
 Scarring/Disfigurement Poor cosmetic result or excess skin removal	Severity (Consult definitions for grading classification)	Events/AE Code (Consult definitions for codes)
	Mild 	
	Moderate 	
	Severe 	
 Device Displacement	Moderate or Severe AE	Relationship to Device
 Device detachment	Yes  No 	Unrelated 
 Infection	If "Yes," complete adverse events form	Possibly 
 Injury to penis		Definitely 
 Sexual effects/ undesirable sensory changes		
 Wound Disruption	Action	Pain VAS (see below)
 Excess swelling of penis/scrotum	None  Pharmaceutical 	
 Hematoma	Surgical  Non-surgical 	
 Difficulty with removal	Evaluation termination 	

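### The protocol plans to record each AE's relatedness to the circumcision procedure and to the device, but no form shown records relatedness to the procedure, and the device item does not use the protocol's four levels

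*Protocol*

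**What the plan says.** All references are to the Protocol.

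- **Primary Endpoint** (Evaluation Design and Methods), on the description of each AE: "The likelihood of relatedness to having undergone VMMC and relatedness specifically to the ShangRing device will be determined". That is two separate judgements, and no levels are given there.
- **Adverse Event (AE) and Other Device-Related Incident Documentation** prints one four-level scale: definitely related, likely/possibly related, likely unrelated, definitely unrelated. Its lead-in names the device: "AEs that are related to the evaluation device will be graded using the following definitions as guides". Its definitions speak of the procedure: "Definitely related: direct association with the procedure, i.e., follows a reasonable temporal sequence and is a recognized AE of the procedure". The third level reads "Likely unrelated: more likely explained by another cause".
- The same section assigns the record to two forms. For the adverse events form: "The adverse events form will include a description of the onset, duration, relationship to the procedure, severity, seriousness, and final outcome of the AE". For the device-related events form: "This form will include a description of the onset, duration, relationship to the procedure, severity, seriousness, and final outcome of the AE". A physician from another site is to judge each AE's relationship to the procedure.
- **Adverse Events Management** wants moderate, severe and serious AEs reported even when they do not appear related to the procedure.
- **Analysis Overview**: "Adverse event rates will be presented by seriousness, severity, relation to device and outcome by site and by cadre".
- **Appendix XVIII**: the Device Events Form has one item, "Relationship to Device", with the boxes Unrelated, Possibly and Definitely. The Adverse Events (AE) Form has no relatedness item. It carries a Device Event Number.

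**The concern.** The text promises a judgement on relationship to the procedure on two named forms, and neither form has a place for it. The one relatedness item that exists concerns the device and uses a different scale from the text.

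This matters because the primary endpoint is worded as AEs associated with ShangRing circumcision procedures, while apparently unrelated moderate, severe and serious events are reported as well. Relationship to the procedure is the judgement that separates these two groups. The clinical data come from standardized forms, and the data entry screens follow the form questions, so a judgement without a field has no planned route into the database. An analysis plan cannot supply it later. It would have to be reconstructed retrospectively from notes.

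**Working it through.** No figure in the protocol depends on this point, so the check sets text and forms side by side. The body text cites older appendix numbers for the AE forms, so forms were matched by title.

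**1. What is required and what the forms hold**

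| Item | Text | Device Events Form | Adverse Events (AE) Form |
|---|---|---|---|
| Relationship to procedure | Required; promised on both forms | Absent | Absent |
| Relationship to device | Required | Present, three boxes | Absent; can be looked up by Device Event Number |
| Number of levels | Four | Three | None |

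**2. Other forms.** The national client form (Appendix VIII), the ShangRing device form (Appendix IX) and the follow-up form (Appendix XII) record whether an AE occurred and how severe it was, but not relatedness. The day-3 post-removal call form (Appendix XIV) records symptoms only.

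**3. Mapping the four levels onto the three boxes.** Definitely related goes to Definitely, likely/possibly related to Possibly, and definitely unrelated to Unrelated. Likely unrelated has no box of its own. Ticked as Unrelated, it merges with the definitely unrelated events. Ticked as Possibly, it merges with the likely/possibly related ones. Either way the level is lost.

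**4. What can and cannot be produced from the forms shown**

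- Overall AE rate: yes. The documentation section builds it from all mild, moderate and severe events, and the Analysis Overview defines it as the percentage of clients with at least one AE. Neither applies a relatedness filter.
- AE rates by relation to device: yes, on three levels. The Device Events Form covers all severities, and the Device Event Number links the moderate and severe events.
- AEs by relatedness to the procedure, as planned under Primary Endpoint: no.
- Separating apparently unrelated reported events from those associated with the procedure: no.
- Likely unrelated against definitely unrelated: no.

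**5. Scale.** At the protocol's assumed 2%, 0.02 × 575 = 11.5 clients would have an AE. One client placed in a different row of a relatedness table moves that row by 1/575 = 0.17 percentage points. The documents do not say how many events would be hard to classify, so no overall shift can be derived.

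**The case against.** The strongest defence is that little of the planned analysis is blocked. The AE rate needs no relatedness judgement. The only relatedness table named in the Analysis Overview is by relation to device, and the forms support it on three levels. The Device Event Number partly makes up for the missing item on the Adverse Events Form. The methods for assessing relatedness are said to be in the SOP manual, which is not shown and might contain a further record of the physician's judgement. Many event types in Appendix XIX are tied to the procedure or the device by definition.

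Most of this stands, and it limits the point. It does not remove the mismatch. The protocol names these two forms as the place where relationship to the procedure is recorded, and they do not record it. The link by number recovers only the three-level device answer.

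A reader might also infer more than the documents support:

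- *That four levels are required for both judgements.* The scale is printed once, with a device lead-in and procedure-worded definitions. The Primary Endpoint section sets no levels.
- *That the primary rate cannot be calculated, or shifts by a known amount.* The rate has no relatedness filter, and any number of misclassified events would be invented.
- *That an anaesthetic reaction could only be ticked as unrelated to the device.* There is a Possibly box, and the event type and time of occurrence on the same form already mark it as procedural.

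**Conclusion.** The text and the forms contradict each other, and data planned under the primary endpoint would not be captured on any form shown. The size is one of two relatedness judgements missing, one of four levels without a box, and no relatedness item on the Adverse Events Form. The consequence is limited to describing AEs by relatedness. The overall AE rate and a coarser device table remain available.

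This rests on the forms as reproduced in the appendices. It assumes that neither the SOP manual, which is not shown, nor a log whose table did not survive in the text (such as Appendix XV) holds a separate structured record of relationship to the procedure. If one does, the protocol should name it in place of the two forms.

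**What to change.** Before data collection starts:

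1. On the Device Events Form, replace the single device item with two items, relationship to the procedure and relationship to the device, each with the four levels in the documentation section.
2. Repeat both items on the Adverse Events Form, or state that they are carried over through the Device Event Number.
3. Have both completed from the evaluating physician's assessment, and extend that assessment to the device, since the documentation section now mentions only the procedure.
4. In the documentation section, say which judgement the scale grades. If it grades both, word the definitions for each.
5. Keep the AE rate over all mild, moderate and severe events, and tabulate AEs by procedure relatedness and by device relatedness alongside it. Restricting the primary rate to related events is not needed here. It would be a separate and debatable choice, because it could shrink a safety numerator.

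The cost is one added tick-box row and one revised row, the matching database variables, and a short edit to the text. The procedure judgement is already required of the physician. Left until after data collection, it could only be reconstructed retrospectively.
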